# Table 38:Number and Percentage of Subjects Experiencing Solicited Events Post Any Vaccination by Symptom, Study Arm, and Sex -
Safety Population

		Liquid (N	AV7909 =X)			Lyophiliz (N	ed AV7909 =X)			All Subjects (N=X)		
	Fen	nale	M	lale	e Female Male			ale	Female		M	ale
Symptom	n	%	n	%	n	%	n	%	n	%	n	%
				All S	Symptoms							
Any Symptom	X	x	x	x	x	х	x	Х	х	х	x	x
		·	·	System	ic Sympto	ms	·				·	·
Any Systemic Symptom	x	x	x	x	x	х	x	Х	Х	х	x	x
Fever	x	x	x	x	x	х	x	Х	Х	х	x	x
Feverishness	x	х	x	x	x	х	x	Х	х	х	x	x
Fatigue												
Malaise												
Myalgia												
Arthralgia												
Headache												
Nausea												
				Injection	Site Symp	toms	·				·	·
Any Injection Site Symptom	X	x	x	x	x	х	x	Х	х	х	x	x
Pain	X	x	x	x	x	х	x	Х	х	х	x	x
Tenderness	x	x	x	x	x	х	x	х	х	х	x	x
Pruritus												
Ecchymosis												
Ecchymosis (measurement)												
Erythema												
Erythema (measurement)												

### Table 38:Number and Percentage of Subjects Experiencing Solicited Events Post Any Vaccination by Symptom, Study Arm, and Sex - Safety
Population (continued)

	Liquid AV7909 (N=X)				Lyophilized AV7909 (N=X)				All Subjects (N=X)			
	Fen	nale Male Female Ma			ale	Female		Male				
Symptom	n	%	n	n %		%	n	%	n	%	n	%
Edema/Induration												
Edema/Induration (measurement)												
Notes: N = Number of subjects in the safet a Exact binomial confidence interval calcul	Addition (measurement)       Image: Inditiation (measurement)         Jotes: N = Number of subjects in the safety population who received the first study vaccination; n = Number of subjects with reported event.         Exact binomial confidence interval calculated using Clopper-Pearson methodology.										•	

Tables with similar format:

## Table 39:Number and Percentage of Subjects Experiencing Solicited Events Post Any Vaccination by Symptom, Study Arm, and Age
Category - Safety Population

[Implementation Note: Replace "Female" and "Male" with "Age 18-30" and "Age 31-45".]

		Liq	uid AV7909 (N=X)	Lyophi	lized AV7909 (N=X)	All	Subjects (N=X)
Symptom	Severity	n	% (95% CI) a	Lyophilized AV7909 (N=X)           n         % (95% CI) a s	% (95% CI) a	n	% (95% CI) a
	· · ·		All Symptoms				
Any Symptom	None	х	x (x.x, x.x)	х	x (x.x, x.x)	Х	x (x.x, x.x)
	Mild						
	Moderate						
	Severe						
	·		Systemic Symptoms				·
Any Systemic Symptom	None	х	x (x.x, x.x)	Х	x (x.x, x.x)	Х	x (x.x, x.x)
	Mild						
	Moderate						
	Severe						
Fever	None	X	x (x.x, x.x)	X	x (x.x, x.x)	Х	x (x.x, x.x)
	Mild						
	Moderate						
	Severe						
Feverishness	None	Х	x (x.x, x.x)	Х	x (x.x, x.x)	Х	x (x.x, x.x)
	Mild						
	Moderate						
	Severe						
Fatigue	None	Х	x (x.x, x.x)	Х	x (x.x, x.x)	X	x (x.x, x.x)
	Mild						
	Moderate						
	Severe						
Malaise	None	х	x (x.x, x.x)	Х	x (x.x, x.x)	X	x (x.x, x.x)
	Mild						

# Table 40:Number and Percentage of Subjects Experiencing Solicited Events Post First Vaccination by Symptom, Maximum Severity and
Study Arm - Safety Population

- 83 -

		Liq	uid AV7909 (N=X)	Lyophi	ilized AV7909 (N=X)	All Subjects (N=X)		
Symptom	Severity	n	% (95% CI) a	n	% (95% CI) a	n	% (95% CI) a	
	Moderate							
	Severe							
Myalgia	None	х	x (x.x, x.x)	Х	x (x.x, x.x)	х	x (x.x, x.x)	
	Mild							
	Moderate							
	Severe							
Arthralgia	None	х	x (x.x, x.x)	Х	x (x.x, x.x)	х	x (x.x, x.x)	
	Mild							
	Moderate							
	Severe							
Headache	None	х	x (x.x, x.x)	Х	x (x.x, x.x)	х	x (x.x, x.x)	
	Mild							
	Moderate							
	Severe							
Nausea	None	х	x (x.x, x.x)	Х	x (x.x, x.x)	х	x (x.x, x.x)	
	Mild							
	Moderate							
	Severe							
			Injection Site Symptom	15				
Any Injection Site Symptom	None	х	x (x.x, x.x)	Х	x (x.x, x.x)	Х	x (x.x, x.x)	
	Mild							
	Moderate							
	Severe							
Pain	None	Х	x (x.x, x.x)	х	x (x.x, x.x)	х	x (x.x, x.x)	

### Table 40: Number and Percentage of Subjects Experiencing Solicited Events Post First Vaccination by Symptom, Maximum Severity and Study Arm – Safety Population (continued)

- 84 -

		Liq	uid AV7909 (N=X)	Lyophi	ilized AV7909 (N=X)	AI	l Subjects (N=X)
Symptom	Severity	n	% (95% CI) a	n	% (95% CI) a	n	% (95% CI) a
	Mild						
	Moderate						
	Severe						
Tenderness	None	x	x (x.x, x.x)	х	x (x.x, x.x)	Х	x (x.x, x.x)
	Mild						
	Moderate						
	Severe						
Pruritus	None	X	x (x.x, x.x)	х	x (x.x, x.x)	Х	x (x.x, x.x)
	Mild						
	Moderate						
	Severe						
Ecchymosis	None	X	x (x.x, x.x)	Х	x (x.x, x.x)	Х	x (x.x, x.x)
	Mild						
	Moderate						
	Severe						
Ecchymosis (measurement)	None	X	x (x.x, x.x)	х	x (x.x, x.x)	Х	x (x.x, x.x)
	Mild						
	Moderate						
	Severe						
Erythema	None	X	x (x.x, x.x)	х	x (x.x, x.x)	Х	x (x.x, x.x)
	Mild						
	Moderate						
	Severe						
Erythema (measurement)	None	X	x (x.x, x.x)	X	x (x.x, x.x)	X	x (x.x, x.x)

### Table 40: Number and Percentage of Subjects Experiencing Solicited Events Post First Vaccination by Symptom, Maximum Severity and Study Arm – Safety Population (continued)

- 85 -

RESTRICTED

		Liqu	id AV7909 (N=X)	Lyophi	lized AV7909 (N=X)	All	Subjects (N=X)
Symptom	Severity	n	% (95% CI) a	n	% (95% CI) a	n	% (95% CI) a
	Mild						
	Moderate						
	Severe						
Edema/Induration	None	X	x (x.x, x.x)	Х	x (x.x, x.x)	Х	x (x.x, x.x)
	Mild						
	Moderate						
	Severe						
Edema/Induration (measurement)	None	x	x (x.x, x.x)	Х	x (x.x, x.x)	Х	x (x.x, x.x)
	Mild						
	Moderate						
	Severe						
Notes: N = Number of subjects a a Exact binomial confidence inte	in the safety populati rval calculated using	on who received the f Clopper-Pearson met	irst study vaccination; n = N hodology.	lumber of subjects	with reported event.		

### Table 40: Number and Percentage of Subjects Experiencing Solicited Events Post First Vaccination by Symptom, Maximum Severity and Study Arm – Safety Population (continued)

Tables with similar format:

### Table 41:Number and Percentage of Subjects Experiencing Solicited Events Post Second Vaccination by Symptom, Maximum Severity,
and Study Arm - Safety Population

[Implementation Note: Update N footnote to "...who received the second study vaccination"]

Table 42:Number and Percentage of Subjects Experiencing Solicited Events Post Any Vaccination by Symptom, Maximum Severity, and
Study Arm - Safety Population

[Implementation Note: Update N footnote to "...who received any study vaccination"]

Symptom	Severity	Pre-	Dose	Post	-Dose	Da	ıy 1	D	ay 2	Da	y 3	Da	y 4	Da	y 5	Da	ny 6	Da	ıy 7	Day	7 8 +
		n	%	n	%	n	%	n	%	n	%	n	%	n	%	n	%	n	%	n	%
		1				All S	ympton	ns					1	L							
Any Symptom	None																				
	Mild																				
	Moderate																				
	Severe																				
					S	ystemi	e Symp	toms		-							-				
Any Systemic Symptoms	None																				
	Mild																				
	Moderate																				
	Severe																				
Fever	None	N/A	N/A	N/A	N/A																
	Mild	N/A	N/A	N/A	N/A																
	Moderate	N/A	N/A	N/A	N/A																
	Severe	N/A	N/A	N/A	N/A																
Feverishness	None																				
	Mild																				
	Moderate																				
	Severe																				
Fatigue	None																				
	Mild																				
	Moderate																				
	Severe																			1	

# Table 43:Number and Percentage of Subjects Experiencing Solicited Events by Symptom, Severity, and Day Post First Vaccination -
Liquid AV7909, Safety Population

- 87 -

Symptom	Severity	Pre-	Dose	Post-	-Dose	Da	ıy 1	Da	ny 2	Da	y 3	Da	y 4	Da	y 5	Da	y 6	Da	y 7	Day	8 +
		n	%	n	%	n	%	n	%	n	%	n	%	n	%	n	%	n	%	n	%
Malaise	None																				
	Mild																				
	Moderate																				
	Severe																				
Myalgia	None																				
	Mild																				
	Moderate																				
	Severe																				
Arthralgia	None																				
	Mild																				
	Moderate																				
	Severe																				
Headache	None																				
	Mild																				
	Moderate																				
	Severe																				
Nausea	None																				
	Mild																				
	Moderate																				
	Severe																				
					Inje	ction S	ite Syn	nptoms													
Any Injection Site Symptom	None																				

### Table 43: Number and Percentage of Subjects Experiencing Solicited Events by Symptom, Severity, and Day Post First Vaccination - Liquid AV7909, Safety Population (continued)

- 88 -

Symptom	Severity	Pre-	-Dose	Post	-Dose	Da	ıy 1	Da	ay 2	Da	y 3	Da	y 4	Da	y 5	Da	ny 6	Da	ıy 7	Day	y 8 +
		n	%	n	%	n	%	n	%	n	%	n	%	n	%	n	%	n	%	n	%
	Mild																				
	Moderate																				
	Severe																				
Pain	None																				
	Mild																				
	Moderate																				
	Severe																				
Tenderness	None																				
	Mild																				
	Moderate																				
	Severe																				
Pruritus	None																				
	Mild																				
	Moderate																				
	Severe																				
Ecchymosis	None																				
	Mild																				
	Moderate																				
	Severe																				
Ecchymosis (measurement)	None																				
	Mild																				
	Moderate																				

#### Table 43: Number and Percentage of Subjects Experiencing Solicited Events by Symptom, Severity, and Day Post First Vaccination - Liquid AV7909, Safety Population (continued)

- 89 -

Symptom	Severity	Pre-	Dose	Post	-Dose	Da	ıy 1	Da	ny 2	Da	y 3	Da	y 4	Da	y 5	Da	ny 6	Da	y 7	Day	7 8 +
		n	%	n	%	n	%	n	%	n	%	n	%	n	%	n	%	n	%	n	%
	Severe																				
Erythema	None																				
	Mild																				
	Moderate																				
	Severe																				
Erythema (measurement)	None																				
	Mild																				
	Moderate																				
	Severe																				
Induration/Swelling	None																				
	Mild																				
	Moderate																				
	Severe																				
Induration/Swelling (measurement)	None																				
	Mild																				
	Moderate																				
	Severe																				
Notes: N = Number of subjects in the Symptoms were solicited in clinic is refers to events reported on Day 1 v	he safety population mmediately before a via Memory Aid.	who re ind afte	ceived r dosin	the fir g ("Pre	st study e-Dose'	vacci and"l	nation; Post-Do	n = N ose" co	umber olumns	of sub ) and v	jects v ia Me	vith rep mory 2	oorted Aid ov	event. er the	follow	ving 8	days. T	The "I	)ay 1"	' colur	nn

#### Table 43: Number and Percentage of Subjects Experiencing Solicited Events by Symptom, Severity, and Day Post First Vaccination - Liquid AV7909, Safety Population (continued)

Severity is the maximum severity reported post dosing for each subject for each day.

Tables with similar format:

- Table 44:Number and Percentage of Subjects Experiencing Solicited Events by Symptom, Severity, and Day Post First Vaccination -
Lyophilized AV7909, Safety Population
- Table 45:Number and Percentage of Subjects Experiencing Solicited Events by Symptom, Severity, and Day Post Second Vaccination -
Liquid AV7909, Safety Population

[Implementation Note: Update N footnote to "...who received the second study vaccination"]

Table 46:Number and Percentage of Subjects Experiencing Solicited Events by Symptom, Severity, and Day Post Second Vaccination -
Lyophilized AV7909, Safety Population

[Implementation Note: Update N footnote to "...who received the second study vaccination"]

Study Arm		Dose 2 - No Symptoms	Dose 2 - Mild or Greater Symptoms	Dose 2 - Total
		n (%)	n (%)	n (%)
		Systemic Symptoms		
Liquid AV7909	Dose 1 - No Symptoms	x (%)	x (%)	x (%)
(N=X)	Dose 1 - Mild or Greater Symptoms	x (%)	x (%)	x (%)
	Dose 1 - Total	x (%)	x (%)	x (100%)
Lyophilized AV7909	Dose 1 - No Symptoms	x (%)	x (%)	x (%)
(N=X)	Dose 1 - Mild or Greater Symptoms	x (%)	x (%)	x (%)
	Dose 1 - Total	x (%)	x (%)	x (100%)
		Injection Site Sympto	ms	
Liquid AV7909	Dose 1 - No Symptoms	x (%)	x (%)	x (%)
(N=X)	Dose 1 - Mild or Greater Symptoms	x (%)	x (%)	x (%)
	Dose 1 - Total	x (%)	x (%)	x (100%)
Lyophilized AV7909	Dose 1 - No Symptoms	x (%)	x (%)	x (%)
(N=X)	Dose 1 - Mild or Greater Symptoms	x (%)	x (%)	x (%)
	Dose 1 - Total	x (%)	x (%)	x (100%)
Notes: N = Number of s Denominators for perce	subjects in the safety population; $n = Numl$ ntages are the number of subjects in the sa	per of subjects with reported event. fety population who received the fi	rst and second dose of study vaccination.	

## Table 47:Number and Percentage of Subjects Experiencing Solicited Events for Dose 1 Compared with Dose 2 by Study Arm - Safety
Population

#### 14.3.1.2 Unsolicited Adverse Events

### Table 48:Number and Percentage of Subjects Experiencing Unsolicited Adverse Events with 95% Confidence Intervals by MedDRA
System Organ Class and Preferred Term, and Study Arm - Safety Population

			Liquid AV7909 (N=X)	)		Lyophilized AV79 (N=X)	09		All Subjects (N=X)	
MedDRA System Organ Class	MedDRA Preferred Term	n	% (95% CI) a	Events	n	% (95% CI) a	Events	n	% (95% CI) a	Events
Any SOC	Any PT	X	xx (xx.x, xx.x)	х	х	xx (xx.x, xx.x)	х	х	xx (xx.x, xx.x)	Х
[SOC 1]	Any PT	X	xx (xx.x, xx.x)	х	X	xx (xx.x, xx.x)	Х	X	xx (xx.x, xx.x)	Х
	[PT 1]	X	xx (xx.x, xx.x)	х	X	xx (xx.x, xx.x)	х	X	xx (xx.x, xx.x)	Х
	[PT 2]									
[SOC 2]	Any PT									
	[PT 1]									
	[PT 2]									
Notes: N = Number of subjects a Exact binomial confidence into	in the safety population; n = erval calculated using Clopp	Number er-Pearso	of subjects with rep n methodology.	oorted event;	Events =	Total frequency of	events repor	ted.		

					Liquid (N	AV790   = X)	9			Lyo	ophiliz (N	ed AV7 = X)	909				All S (N	ubjects = X)		
			Re	lated	N Re	Not lated	Та	otal	Re	lated	N Rel	lot ated	T	otal	Rel	ated	N Rel	lot lated	Та	otal
MedDRA System Organ Class	MedDRA Preferred Term	Severity	n	%	n	%	n	%	n	%	n	%	n	%	n	%	n	%	n	%
Any SOC	Any PT	Any Severity	x	XX	x	XX	X	xx	х	xx	х	XX	x	xx	x	xx	х	XX	x	xx
		Mild	x	XX	x	XX	х	XX	х	xx	х	XX	x	XX	x	xx	х	XX	х	XX
		Moderate	x	XX	x	XX	X	xx	х	xx	х	XX	x	xx	x	xx	х	XX	x	xx
		Severe	x	xx	x	XX	х	xx	х	xx	х	XX	x	XX	x	xx	х	XX	х	xx
[SOC 1]	[PT 1]	Any Severity	x	XX	x	XX	х	XX	х	xx	х	XX	x	XX	x	xx	х	XX	х	XX
		Mild	x	xx	x	XX	х	xx	х	xx	х	XX	x	XX	x	xx	х	XX	х	xx
		Moderate																		
		Severe																		
	[PT 2]	Any Severity																		
		Mild																		
		Moderate																		
		Severe																		

## Table 49:Unsolicited Adverse Events by MedDRA System Organ Class and Preferred Term, Maximum Severity, Relationship, and Study
Arm - Safety Population

# Table 50:Number and Percentage of Subjects Experiencing Unsolicited Adverse Events by MedDRA System Organ Class and Preferred
Term, Severity, and Relationship - Safety Population

						Sev	erity			Rela	tionship	to Treat	ment
		Any Ir	cidence	N	lild	Mod	lerate	Se	vere	Not R	elated	Re	ated
MedDRA System Organ Class	MedDRA Preferred Term	n	%	n	%	n	%	n	%	n	%	n	%
	·		Liquid	AV7909	(N=X)								
Any SOC	Any PT	X	xx	x	XX	x	XX	x	XX	x	XX	X	XX
[SOC 1]	Any PT	X	xx	x	xx	X	XX	x	XX	x	XX	X	xx
	[PT 1]	X	xx	x	xx	x	XX	x	XX	x	XX	x	XX
	[PT 2]												
[SOC 2]	Any PT												
	[PT 1]												
	[PT 2]												
		I	yophilize	ed AV79	09 (N=X)								
Any SOC	Any PT	X	xx	x	xx	x	XX	x	xx	x	XX	X	XX
[SOC 1]	Any PT	X	xx	x	xx	x	XX	x	XX	x	XX	X	XX
	[PT 1]	X	xx	x	xx	x	XX	x	xx	x	XX	x	xx
	[PT 2]												
[SOC 2]	Any PT												
	[PT 1]												
	[PT 2]												
Notes: N = Number of subjects in A subject is counted only once per	the safety population; n = Number PT and is summarized according	of subject to their hi	ts with re ghest seve	ported ev erity and	ent. closest rela	ationship					•	•	.

#### 14.3.2 Listing of Deaths, Other Serious and Significant Adverse Events

#### Table 51: Listing of Serious Adverse Events - Safety Population

Adverse Event	Associated with Dose No.	No. of Days Post Associated Dose (Duration)	No. of Days Post Dose the Event Became Serious (Duration)	Reason Reported as an SAE	Severity	Relationship to Study Treatment	If Not Related, Alternative Etiology	Action Taken with Study Treatment	Subject Discontinued Due to AE	Outcome	MedDRA System Organ Class	MedDRA Preferred Term
Subject II	D: ; Study Arı	n: ; AE Numl	ber:									
Comments	5:								·			
Subject II	D: ; Study Arı	n: ; AE Numl	ber:									
Comments	5:	•	•	•	•	•		•	•	•		•

Adverse Event	Associated with Dose No.	No. of Days Post Associated Dose (Duration)	Severity	Relationship to Study Treatment	If Not Related, Alternative Etiology	Action Taken with Study Treatment	Subject Discontinued Due to AE?	Outcome	MedDRA System Organ Class	MedDRA Preferred Term
Subject ID: , S	Study Arm: , AE	Number:								
Comments:										
Subject ID: , S	Study Arm: , AE	Number:								
Comments:							 			

#### Table 52: Listing of Non-Serious, Unsolicited, Moderate or Severe Adverse Events - Safety Population

Adverse Event	Associated with Dose No.	No. of Days Post Associated Dose (Duration)	SAE? (Severity)	Relationship to Study Treatment	If Not Related, Alternative Etiology	Action Taken with Study Treatment	Subject Discontinued Due to AE?	Outcome	PIMMC/ AESI?	MAAE?	MedDRA System Organ Class	MedDRA Preferred Term
Subject ID:	, Study Arm	:, AE Number	r:									
			Yes/No				Yes/No		Yes/No	Yes/No		
			(Severity)									
Comments:												
Subject ID:	: , Study Arm	:, AE Number	r:									
			Yes/No				Yes/No		Yes/No	Yes/No		
			(Severity)									
Comments:												

#### Table 53: Listing of Other Significant Adverse Events - Safety Population

### 14.3.3 Narratives of Deaths, Other Serious and Significant Adverse Events

(not included in SAP, but this is a placeholder for the CSR)

### 14.3.4 Abnormal Laboratory Value Listings (by Subject)

#### Table 54: Listing of Abnormal Laboratory Results - Chemistry, Safety Population

Subject ID	Study Arm	Sex	Age (years)	Planned Study Day	Actual Study Day	Laboratory Parameter (Units)	Result (Severity)	Relationship to Treatment	If Not Related, Alternate Etiology	Action Taken with Study Treatment	Subject Discontinued Due to Result?

Table 55:Listing of Abnormal Laboratory Res	sults - Hematology, Safety Population
---	---------------------------------------

Subject ID	Study Arm	Sex	Age (years)	Planned Study Day	Actual Study Day	Laboratory Parameter (Units)	Result (Severity)	Relationship to Treatment	If Not Related, Alternate Etiology	Action Taken with Study Treatment	Subject Discontinued Due to Result?

### Table 56: Listing of Abnormal Laboratory Results - Urinalysis, Safety Population

Subject ID	Study Arm	Sex	Age (years)	Planned Study Day	Actual Study Day	Laboratory Parameter (Units)	Result (Severity)	Relationship to Treatment	If Not Related, Alternate Etiology	Action Taken with Study Treatment	Subject Discontinued Due to Result?

#### 14.3.5.1 **Chemistry Results**

[General Implementation Note: Red text is included as a placeholder; this text should NOT be included in the following tables unless instructed in the individual table's corresponding implementation note.]

#### Table 57: Laboratory Results by Parameter, Maximum Severity, Study Day, and Study Arm - Any Chemistry Parameter, Safety Population

[Implementation Note:

1) Include "Day 64a" rows.

2) Include footnote, "AST and random glucose collection were no longer required following the finalization of protocol version 4.0." 3) Include footnote, "a Safety laboratories are not scheduled for collection at Day 64, but any results collected at this visit are reported."]

		N	one	M Gr	ild / ade 1	Mod Gra	erate / nde 2	Sev Gra	ere / 1de 3
Study Arm	Ν	n	%	n	%	n	%	n	%
Liquid AV7909	X	x	XX	x	XX	х	XX	х	XX
Lyophilized AV7909									
Liquid AV7909									
Lyophilized AV7909									
Liquid AV7909									
Lyophilized AV7909									
Liquid AV7909									
Lyophilized AV7909									
	Study ArmLiquid AV7909Lyophilized AV7909Liquid AV7909Lyophilized AV7909Lyophilized AV7909Liquid AV7909Lyophilized AV7909Lyophilized AV7909Lyophilized AV7909Liquid AV7909Liquid AV7909Liquid AV7909	Study ArmNLiquid AV7909xLyophilized AV7909Liquid AV7909Lyophilized AV7909Lyophilized AV7909Liquid AV7909Liquid AV7909Lyophilized AV7909Lyophilized AV7909Lyophilized AV7909Liquid AV7909Liquid AV7909Liquid AV7909Liquid AV7909Lyophilized AV7909	Study ArmNLiquid AV7909xLyophilized AV7909Liquid AV7909Lyophilized AV7909Lyophilized AV7909Lyophilized AV7909Liquid AV7909Liquid AV7909Lyophilized AV7909Lyophilized AV7909Lyophilized AV7909Lyophilized AV7909Liquid AV7909Liquid AV7909Liquid AV7909Lyophilized AV7909	Study ArmNnLiquid AV7909xxLyophilized AV7909Liquid AV7909Liquid AV7909Lyophilized AV7909Lyophilized AV7909Lyophilized AV7909Liquid AV7909Liquid AV7909Liquid AV7909Liquid AV7909Lyophilized AV7909Liquid AV7909Liquid AV7909Lyophilized AV7909<	Study ArmNnMLiquid AV7909xxxxLyophilized AV7909 </td Study ArmNnMild / Grade 1Liquid AV7909xxxxxLyophilized AV7909IIIILiquid AV7909IIIIILiquid AV7909IIIIILiquid AV7909IIIIILyophilized AV7909IIIIILiquid AV7909IIIIILiquid AV7909IIIIILiquid AV7909IIIIILyophilized AV7909IIIIILiquid AV7909IIIIILiquid AV7909IIIIILiquid AV7909IIIIILiquid AV7909IIIIILiquid AV7909IIIIILiquid AV7909IIIIILiquid AV7909II<td< td="">Study Arm       N       N       %       Mil / Grade       Mode Grade         I iquid AV7909       N       N       %       N       %       N       N       N       N       N       Mode Grade       N	Figure 1NodestigationNo<th< td="">Kith         Moderate /         Seven           Study Arm         N         <math>n</math> <math>n</math><!--	</th<>	</td<>	Study ArmNnMild / Grade 1Liquid AV7909xxxxxLyophilized AV7909IIIILiquid AV7909IIIIILiquid AV7909IIIIILiquid AV7909IIIIILyophilized AV7909IIIIILiquid AV7909IIIIILiquid AV7909IIIIILiquid AV7909IIIIILyophilized AV7909IIIIILiquid AV7909IIIIILiquid AV7909IIIIILiquid AV7909IIIIILiquid AV7909IIIIILiquid AV7909IIIIILiquid AV7909IIIIILiquid AV7909II <td< td="">Study Arm       N       N       %       Mil / Grade       Mode Grade         I iquid AV7909       N       N       %       N       %       N       N       N       N       N       Mode Grade       N	Figure 1NodestigationNo<th< td="">Kith         Moderate /         Seven           Study Arm         N         <math>n</math> <math>n</math><!--	</th<>	</td<>	Study Arm       N       N       %       Mil / Grade       Mode Grade         I iquid AV7909       N       N       %       N       %       N       N       N       N       N       Mode Grade       N	Figure 1NodestigationNo <th< td="">Kith         Moderate /         Seven           Study Arm         N         <math>n</math> <math>n</math><!--	</th<>	Kith         Moderate /         Seven           Study Arm         N $n$ </td

umber of subjects in the safety population with available data at the corresponding time point; N is the denominator for percentages.

The "Max Severity Post Baseline" rows indicate the maximum severity experienced by each subject at any time point post baseline, including unscheduled assessments. If a subject has only ungraded results post baseline, their maximum severity is considered "None".

[LAB NAME] collection was no longer required following the finalization of protocol version 4.0.

Safety laboratories are not scheduled for collection at Day 64, but any results collected at this visit are reported.

Tables with similar format:

- Table 58:Laboratory Results by Parameter, Maximum Severity, Study Day, and Study Arm Alkaline Phosphatase (ALP), Safety
Population
- Table 59:Laboratory Results by Parameter, Maximum Severity, Study Day, and Study Arm Alanine Transaminase (ALT), Safety
Population
- Table 60:Laboratory Results by Parameter, Maximum Severity, Study Day, and Study Arm Aspartate Aminotransferase (AST), Safety
Population

[Implementation Note: Include footnote, "AST collection was no longer required following the finalization of protocol version 4.0."]

- Table 61:
   Laboratory Results by Parameter, Maximum Severity, Study Day, and Study Arm Total Bilirubin, Safety Population
- Table 62:Laboratory Results by Parameter, Maximum Severity, Study Day, and Study Arm -Blood Urea Nitrogen (BUN), Safety
Population
- Table 63:
   Laboratory Results by Parameter, Maximum Severity, Study Day, and Study Arm Creatinine, Safety Population

 Table 64:
 Laboratory Results by Parameter, Maximum Severity, Study Day, and Study Arm - Random Glucose, Safety Population

[Implementation Notes:

- 1) Include "Day 64a" rows.
- 2) Include footnote, "Random glucose collection was no longer required following the finalization of protocol version 4.0."
- 3) Include footnote, "a Safety laboratories are not scheduled for collection at Day 64, but any results collected at this visit are reported."]

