## 9 ASSESSMENT OF SAFETY

## 9.1 Specification of Safety Parameters

Safety will be assessed by the frequency and severity of the following:

- 1. SAEs occurring from the time of the first study vaccination through approximately 12 months after the second study vaccination (approximately Day 380).
- 2. Solicited AEs reactogenicity events occurring from the time of each study vaccination (Day 1) through Day 8 after each study vaccination (or until resolved):
  - a) Injection site reactions including pruritus, ecchymosis, erythema, edema/induration, pain, and tenderness.
  - b) Systemic reactions including fever, feverishness, fatigue, malaise, myalgia, arthralgia, headache, and nausea.
- 3. Clinical safety laboratory AEs occurring from the time of the first study vaccination through approximately Day 29. Parameters are found in Table 10.
- 4. Unsolicited AEs –non-serious unsolicited AEs occurring from the time of the first study vaccination through approximately Day 64.
- 5. AESIs (PIMMCs) and MAAEs occurring from the time of the first study vaccination through approximately Day 380.

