### 3.2. Endpoints

#### 3.2.1. Primary

Safety:

- Occurrence of all SAEs through approximately 12 months following receipt of the second study vaccination (approximately Day 380).
- Occurrence of abnormal clinical safety laboratory AEs at approximately Day 29.
- Occurrence of all protocol specified AESIs (i.e., PIMMCs) and MAAEs, from the time of the first study vaccination through approximately 12 months following the second vaccination (approximately Day 380).
- Occurrence of unsolicited non-serious adverse events from the time of the first study vaccination through approximately Day 64.

Tolerability:

• Occurrence of solicited injection site and systemic reactogenicity events in the week after each study vaccination (Days 1 through 8 and Days 15 through 22, inclusive).

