#### 9.6. Clinical Laboratory Evaluations

Clinical safety laboratory parameters will be collected from each subject prior to the first study vaccination (baseline) and approximately 2 weeks after the second study vaccination (Day 29). Laboratory parameters include blood urea nitrogen (BUN), serum creatinine, alkaline phosphatase, alanine aminotransferase (ALT), total bilirubin, hemoglobin, hemoglobin decrease from baseline, white blood cell (WBC) count, absolute eosinophil count, absolute neutrophil count, and platelets. Additional laboratory parameters were measured under Protocol Version 3.0, including random glucose, aspartate aminotransferase (AST), urine protein, and urine glucose, but collection of these parameters was no longer required after the finalization of Protocol Version 4.0; all available results for these clinical labs are reported, but fewer reported results are expected for these discontinued laboratory measures. The grading scale for clinical laboratory parameters measured under Protocol Version 4.0 is presented in Table 11. The grading scale for additional laboratory parameters measures measured under Protocol Version 3.0 and below (random glucose, AST, urine protein, and urine glucose) is presented in Table 12.

The distribution of laboratory results by severity, study day, and study arm will be presented in Table 57 through Table 64 for chemistry parameters, Table 67 through Table 73 for hematology parameters, and Table 76 through Table 78 for urinalysis parameters. Summaries of abnormal laboratory results related to study product will be presented by severity, study day, and study arm (chemistry: Table 65; hematology: Table 74; urinalysis: Table 79). Descriptive statistics including mean, standard deviation, median, minimum, maximum, and change from baseline will be summarized for each parameter (chemistry: Table 66;

hematology: Table 75; urinalysis: Table 80). Boxplots illustrating the change from baseline for each laboratory parameter will be presented in Figure 21 through Figure 35.

A complete listing of individual clinical laboratory results will be presented in Listing 12, Listing 13, and Listing 14 for chemistry, hematology, and urinalysis, respectively, sorted by study arm, subject ID, parameter, and visit number. Listings of abnormal chemistry, hematology, and urinalysis results will be presented in Table 54, Table 55 and Table 56, respectively.

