# 15. SUMMARY OF CHANGES IN THE CONDUCT OF THE STUDY OR PLANNED ANALYSES

The clinical safety laboratory parameters outlined in Protocol Version 3.0 and below included random glucose, aspartate aminotransferase (AST), urine protein, and urine glucose. At screening, high levels of these laboratory parameters were being collected, resulting in the screen failure of many healthy potential study participants. These laboratory parameters were deemed unnecessary for determining the overall health and eligibility of participants. Random glucose, AST, urine protein, and urine glucose were removed from Protocol Version 4.0 and no longer required for collection from subjects after this protocol amendment. All available clinical laboratory results are reported, but fewer reported results are expected for these discontinued laboratory measures.

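### SAP Tables 57 and 65: the 'Any Chemistry Parameter' rate pools participants tested on seven analytes with participants tested on five, so it is not the rate on the current protocol's panel

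*SAP*

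**What the plan says.** SAP 3.2.1 lists among the primary safety endpoints "Occurrence of abnormal clinical safety laboratory AEs at approximately Day 29". Protocol 9.1 fixes which analytes count: "Parameters are found in Table 10". The chemistry part of that table holds BUN, creatinine, alkaline phosphatase, ALT and total bilirubin, and contains neither AST nor glucose.

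SAP 9.6 gives the same five for chemistry ("Laboratory parameters include blood urea nitrogen (BUN), serum creatinine, alkaline phosphatase, alanine aminotransferase (ALT), total bilirubin") and then adds: "Additional laboratory parameters were measured under Protocol Version 3.0, including random glucose, aspartate aminotransferase (AST), urine protein, and urine glucose". For the discontinued tests it states that "all available results for these clinical labs are reported, but fewer reported results are expected for these discontinued laboratory measures". SAP 15 gives the reason for dropping them: "At screening, high levels of these laboratory parameters were being collected, resulting in the screen failure of many healthy potential study participants".

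The Table 57 shell, for any chemistry parameter, carries the footnote "AST and random glucose collection were no longer required following the finalization of protocol version 4.0". Its N is the number of "subjects in the safety population with available data at the corresponding time point; N is the denominator for percentages". Table 65, on abnormal chemistry results related to treatment, opens with the same composite, lists AST and random glucose among its component rows, and has the same footnote and denominator.

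**The concern.** An 'any abnormality' row means the same thing for every participant only if everyone has the same list of tests. Here the list differs according to which tests were done at each draw. The denominator does not separate the two groups, and a footnote tells the reader that collection changed without making the percentage comparable.

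Estimation is the stated purpose of this trial: SAP sections 5 and 6.8 disclaim hypothesis testing in favour of preliminary estimates. A headline laboratory rate that depends on how many participants happened to receive two discontinued tests is hard to interpret. It also cannot be set against a later study that uses the current panel.

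**Working it through.** The documents state no composite rate and no count of participants tested for AST or glucose, so there is no figure to reproduce. The check has two parts: what enters the composite, and how far that could move the rate.

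**1. Do AST and glucose enter the composite?** The SAP never writes out a definition, so this is an inference, with three supports.
- The AST and glucose footnote is ordered for Table 57 itself. It would have no purpose there if the composite excluded them.
- Table 65 lists both analytes under the same composite.
- The chemistry shells show placeholder content only where a table's own note asks for it. Among Tables 57 to 64, only Table 57 and Table 64 (random glucose) ask for Day 64 rows. By those notes, the composite's Day 64 row can only be filled from glucose.

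**2. Does the denominator correct for this?** No. For a single analyte, N is the participants with that analyte, so Tables 58 to 64 are not mixed. For the composite, a five-test participant and a seven-test participant each add one to N.

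**3. Direction.** For a fixed set of participants, adding analytes to an 'any' rule cannot remove a flag. The all-available rate is therefore at least the five-analyte rate. Bilirubin grading depends on ALT, not AST, so dropping AST leaves the core grades unchanged.

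**4. Size (assumed inputs).** Let p be the flag rate of each core analyte and of AST, g the flag rate of glucose, and f the share with all seven tests. Analytes are taken as independent.

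- Five analytes: r5 = 1 − (1 − p)^5
- Seven analytes: r7 = 1 − (1 − p)^6 × (1 − g)
- Reported: f × r7 + (1 − f) × r5

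For p = 2%, g = 20%: r5 = 1 − 0.98^5 = 9.6%; r7 = 1 − 0.98^6 × 0.80 = 29.1%; at f = 25%, 0.25 × 29.1 + 0.75 × 9.6 = 14.5%.

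| p | g | r5 | r7 | reported, f = 25% | reported, f = 50% |
|---|---|---|---|---|---|
| 1% | 1% | 4.9% | 6.8% | 5.4% | 5.8% |
| 2% | 10% | 9.6% | 20.3% | 12.3% | 14.9% |
| 2% | 20% | 9.6% | 29.1% | 14.5% | 19.4% |
| 5% | 30% | 22.6% | 48.5% | 29.1% | 35.6% |

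The excess runs from about half a point to 13 points across these rows.

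**5. Between arms.** Allocation is 1:1 in variable blocks within four age and sex strata (SAP 4.4.3), so the expected artefact is zero. For the chance part, assume that ten of 40 participants have all seven tests, that they are the earliest in each stratum, split 3/3/2/2, and that blocks are of size 2 (the sizes are not stated). Each stratum of 3 leaves one unpaired participant, so the difference in counts between arms has variance 1 + 1 = 2 and SD 1.41. With the 19.5-point gap (29.1 − 9.6), one participant shifts the arm difference by 19.5/20 = 0.98 points, so the SD is 1.41 × 0.98 = 1.4 points. With blocks of 4, the strata of 2 add 4/3 each: variance 2 + 8/3 = 4.67, SD 2.16, or 2.1 points. Ordinary sampling error at 14.5% with 20 per arm is √(2 × 0.145 × 0.855 / 20) = 11 points.

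**The case against.** The strongest defence is that this is a descriptive summary in a small phase 1 trial and the change is disclosed. SAP 9.6 and 15 state in advance that all available results will be reported and why there will be fewer of some. Chemistry is also shown analyte by analyte (Tables 58 to 64), as summary statistics (Table 66) and in a listing of every abnormal result (Table 54), so a reader can trace any flag that came from AST or glucose. No section names the composite as the estimator of the primary endpoint. Counting every abnormality seen is a conservative habit in safety reporting. All of this stands. It limits the harm to the composite rows of two tables and argues against discarding the extra results. It does not make the composite percentage comparable across participants.

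A reader might infer more than the documents support, in three ways.
- *That the dropped tests must flag often at Day 29.* The remark in SAP 15 is about screening, and the people with high values failed screening. Those enrolled while the tests were required had passed them. The remark gives no Day 29 rate, so the higher values of g above have no basis in the documents.
- *That enrolment date decides the panel.* What matters is the tests done at each draw. Someone enrolled under version 3.0 could reach Day 29 under version 4.0, and a test that is no longer required may still have been done.
- *That the formulation comparison is biased.* It is not in expectation. Blocking keeps the chance component small against sampling error, and SAP 9.6 plans no laboratory test or confidence interval.

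**Conclusion.** The point holds for the absolute level of 'Any Chemistry Parameter' in Tables 57 and 65. That rate mixes a seven-analyte and a five-analyte definition, differs from the panel in Protocol Table 10, and is equal to or higher than the rate on that panel for the same participants. The direction is certain once AST and glucose are in the composite, which the shells strongly imply but the SAP does not spell out.

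The size is unknown. It could be trivial if few participants had the extra tests or if they rarely flagged, and several points or more otherwise; every figure for it here rests on assumed rates and shares. The single-analyte tables and the hematology composite are unaffected. The urinalysis composite lost both its analytes together, so its N is already confined to participants with urine data.

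**What to change.** In SAP 9.6 and Tables 57 and 65:

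- Define the main 'Any Chemistry Parameter' row on the five Protocol Table 10 chemistry analytes (ALP, ALT, total bilirubin, BUN, creatinine) for all participants.
- Add a supplementary row, labelled as including AST and random glucose where measured, and give the number tested for each by arm. The Day 64 composite row belongs here if it holds only glucose.
- Leave Tables 60 and 64 as planned, since they already use only participants with data.

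The cost is one sentence of definition, one programming filter and one extra row. AST or glucose flags move out of the main composite, but they stay visible in the supplementary row, in Tables 60 and 64 and in the Table 54 listing, so no safety information is lost.
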